
## Purpose and Objectives

---

The study will evaluate the effectiveness of a videoconference intervention (VCI) to reduce perinatal depression symptoms (PDS) and anxiety (a highly co-morbid condition) by conducting a randomized controlled trial among women experiencing mild to moderate PDS, as measured by the Edinburgh Postnatal Depression Scale (EPDS). Furthermore, we propose to evaluate differences in response to the VCI between subgroups of childbearing women; Hispanic and North European Descent populations, and rural and urban-dwelling.

Specific aims of the study include:

Aim 1: Evaluate the effectiveness of a VCI to reduce PDS and anxiety, as measured by EPDS and Generalized Anxiety Disorder-7 Item (GAD-7) scores across pregnancy and the postpartum. Methods: Pregnant women of all gestational age up to 6 months postpartum (n = 240) who screen positive for mild to moderate PDS (EPDS scores 9–20) will be randomly assigned to VCI or AC for eight weeks. Both groups will continue with standard care as directed by their primary/prenatal care providers. The EPDS and GAD-7 will be administered at three time points during pregnancy and at 2, 4, and 6 months postpartum. Hypothesis: Women participating in the VCI will have significantly lower post intervention EPDS and GAD-7 scores across pregnancy and postpartum than women in the AC group.

Secondary Aim 1: Explore differences in the effectiveness of the VCI to reduce PDS and anxiety across women who enroll at different stages of their pregnancy or postpartum periods.

Aim 2: Evaluate the interaction of the VCI with specific subgroups: ethnicity (Hispanic, North European descent), geographic location (rural, urban), and the outcome of PDS as measured by EPDS and GAD-7 scores across pregnancy and postpartum. We will oversample in Hispanic and rural populations to ensure sufficient representation from diverse groups. Hypothesis: Women will demonstrate differences in EPDS and GAD-7 scores across pregnancy and postpartum, dependent on their study group membership.

Secondary Aim 2: Explore an additional subgroup analysis, namely between those who are and who are not taking medication at the time of screening.

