#### Participant-Completed Questionnaires

Questionnaires will be completed by participants via a secure, Web-based data management system (REDCap). Women in all study groups will receive an emailed link to the questionnaire. Study questionnaires are to be completed at six time points: T1 = enrollment; T2 = after group session 9; T3 = 2 months post session 9 T4 = 4 months post session 9; T5=6 months post session 9; T6= 8 months post session 9. In addition to participant demographics, questionnaires will include the EPDS as a measure of the primary outcome of interest: depressive symptoms, as well as the GAD-7 as a measure of comorbid anxiety (GAD-7 is a validated survey). To document the standard of care that all participants receive during study participation, the questionnaire at all six-time points also asks participants to report whether they (1) received a diagnosis of depression, anxiety, or other mental health condition; (2) were prescribed or initiated any medication for depression or anxiety; (3) were referred to and/or engaged in mental health services; and/or (4) have engaged in any type of nonpharmacological therapies for depression/anxiety during the study. If a participant does not have an email address, study staff will assist her to establish and access a free email address. All participants will receive instruction on how to access and complete the study questionnaires. The entire questionnaire takes approximately 15 minutes to complete. Participants receive \$20 for each questionnaire completed.

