## **Data Analysis**

We will use multilevel generalized mixed modeling under an intent-to-treat approach to compare the outcome measures of EPDS and GAD-7 between group 1 (VCI) and Group 2 (AC) at six-time points during pregnancy and postpartum. This is an appropriate statistical approach for the described RCT protocol. Sensitivity analysis was conducted with G-Power 3.1. We used RMANOVA with 6 total measures as a conservative power analysis for our mixed-effects model. The sample is powered for the fixed effect of Intervention X Time. For study aim 1: Using RMANOVA with alpha = 0.5, 6 total measures, 0.3 for correlation between repeated measures, and a sample size of 192 total participants gives greater than 90 percent power to detect an effect size of 0.1, which is a net decrease in EPDS and GAD-7 of roughly 1 point decrease per time point, assuming a standard deviation of 5. For study aim 2: For the stratified samples of urban/rural or Hispanic/NED, we have greater than 80 percent power to detect the same Intervention X Time effect size of 0.1.

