### **Data Analysis:**

We will compare demographics, partum group, and medications between groups ( $\chi^2$ ) to document the results of our randomization process. We will further document and test for differences in frequency and means in groups related to additional study-related variables. Examples include dose of participation and birth complications or pre-term deliveries. We will explore the addition of these variables in our analytical models.

We will utilize multilevel generalized mixed modeling (via SPSS and R) under an intent-to-treat (ITT) approach to compare the outcome measures of EPDS and GAD-7 between Group 1 (VCI) and Group 2 (AC) at up to six time points. To assess whether we will need to nest participants within clusters (Level 3, group-level) given that the intervention/control are administered in groups, we will conduct an analysis that adds an additional level (nesting participants within clusters) to our proposed model and calculate the model's ICC. As an exploratory analysis, for both aims, we will add the fixed effect of baby's sex to final models and report results.

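### The power statement describes f = 0.1 as about 1 point per time point, but neither plain reading of that wording gives an Intervention × Time effect of 0.1, and the assumed pattern is not stated

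*Combined protocol and SAP*

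**What the plan says.** The Data Analysis section under Study Procedures names the powered term: "The sample is powered for the fixed effect of Intervention X Time". Its inputs for Aim 1 are given as "Using RMANOVA with alpha = 0.5, 6 total measures, 0.3 for correlation between repeated measures", with 192 participants, an SD of 5 and power above 90 percent. It then puts the detectable effect into points: "an effect size of 0.1, which is a net decrease in EPDS and GAD-7 of roughly 1 point decrease per time point".

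No arm means by visit and no time course of the difference appear anywhere. The Aim 1 hypothesis in Purpose and Objectives gives a direction only: "Women participating in the VCI will have significantly lower post intervention EPDS and GAD-7 scores across pregnancy and postpartum". The Data Analysis section under Statistical Methods says that the mixed model will "compare the outcome measures of EPDS and GAD-7 between Group 1 (VCI) and Group 2 (AC) at up to six time points", again without a pattern.

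The questionnaire schedule begins "T1 = enrollment; T2 = after group session 9; T3 = 2 months post session 9" and runs to T6, so T1 precedes the intervention and five times follow it. EPDS is marked as primary: "questionnaires will include the EPDS as a measure of the primary outcome of interest: depressive symptoms".

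**The concern.** An interaction effect size measures how much the difference between arms changes over time. It cannot be turned into points until the shape of that change is given. One point per time point could mean that the gap grows by a point at each visit, or that it is a point at each visit after the intervention. These are very different effects for an Intervention × Time test.

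At stake is what the trial can claim to detect. Someone judging whether the sample size is adequate, or what a null result would exclude, would rely on the figure in points, because f = 0.1 has no direct clinical meaning.

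**Working it through.** **Inputs.** From the power statement: two arms, six measures, correlation ρ = 0.3, SD 5, N = 192, f = 0.1. From the enrollment goals under Statistical Methods: 1:1 allocation and a total of 240. From Participant-Completed Questionnaires: T1 at enrollment, T2 to T6 afterwards. The expected arm gap at T1 is zero by randomisation. Alpha is printed as 0.5; 0.05 is assumed to be meant, and both were run.

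**Step 1: reproduce the plan's power.** For the repeated-measures interaction, λ = f² × N × 6 / (1 − ρ), with 5 and 5(N − 2) degrees of freedom.
- N = 192: λ = 0.01 × 192 × 6 / 0.7 = 16.46, df 5 and 950. Power is 89.8% at alpha 0.05 and 99.6% at alpha 0.5.
- N = 240: λ = 0.01 × 240 × 6 / 0.7 = 20.57. Power is 95.7% at alpha 0.05.

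The 89.8% agrees with the stated figure to rounding (90% needs N = 194). The other effect-size conventions in the same software give about 65%, so this convention is the one that matches.

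**Step 2: what f = 0.1 means in points.** Let d be the arm gap at each time. With two equal arms, f = (population SD of d over the six times) / (2 × 5). So f = 0.1 is a gap that varies over time with an SD of 10 × 0.1 = 1.0 point.

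**Step 3: candidate patterns** (T1 to T6; power for Intervention × Time at N = 192, alpha 0.05).

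| Arm gap in points | SD of gap | f | Power |
|---|---|---|---|
| 0,1,2,3,4,5 (widening 1 per visit) | 1.708 | 0.171 | >99% |
| 0,1,1,1,1,1 (steady 1 from T2) | 0.373 | 0.037 | 17% |
| 1,1,1,1,1,1 (constant, T1 included) | 0 | 0 | 5% (alpha) |
| 0,0,0,2,2,2 | 1.000 | 0.100 | 90% |
| 0,1,2,3,3,3 | 1.155 | 0.115 | 97% |
| 0,1,2,3,2,1 | 0.957 | 0.096 | 87% |

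At N = 240 the steady 1-point gap has 21% power. Simulation of 4000 trials at N = 192 gave 17% for the steady gap and above 99.9% for the widening gap.

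**Step 4: the reverse calculation.** To reach f = 0.1:
- a steady gap must be 1.0 / 0.373 = 2.68 points from T2;
- a widening gap must grow 1.0 / 1.708 = 0.59 points per visit, or 2.93 points by T6.

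For a steady gap, the powered test at N = 192 needs about 2.4 points for 80% power and 2.7 for 90%.

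**Step 5: does another scale rescue the wording?** Using the within-subject error SD, 5 × √0.7 = 4.18, the two plain readings become 0.204 and 0.045. Neither is 0.1.

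**Step 6: an alternative test, for the optional part of the fix.** For the T1-adjusted mean of T2 to T6, the variance is 25 × [(1 + 4 × 0.3)/5 − 0.3²] = 25 × 0.35 = 8.75. The standard error of the arm difference is √(4 × 8.75/192) = 0.427. Power for 1 point is 64%. The detectable difference is about 1.2 points at 80% power and 1.4 at 90%.

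All figures are before clustering and missing data.

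**The case against.** **The wording is loose, not wrong.** f = 0.1 at SD 5 is exactly a 1.0-point SD of the gap, and the sentence says roughly. Several patterns in the table land on or near 0.1. This stands in part: the sentence can be reconciled with some pattern. But it speaks of a net decrease, not of variation of the gap about its own average, and it describes none of the patterns that fit.

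**The harm rests on the less literal reading.** A decrease per time point most naturally accumulates, and on that reading the plan has more power than it claims. This stands. The Aim 1 hypothesis of lower post-intervention scores is compatible with a steady gap but fixes neither size nor shape, so the 17% is conditional.

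**The test for Aim 1 is clear enough.** A reader might infer that no test has been tied to Aim 1. The documents do not support that in full: the power statement names Intervention × Time, applies it to Aim 1 and uses the same term for Aim 2. What is missing is the assumed pattern, the coding of time and a formal statement that this term decides the aim.

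**The shortfall from 90% is rounding.** This also stands: 89.8% against a claim of more than 90% matters little, and the planned 240 exceeds it.

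**Conclusion.** The translation into points should be corrected. Under neither plain reading does the stated effect match f = 0.1 for the powered term: widening by 1 point per visit is 0.171, and a steady 1-point gap from T2 is 0.037. Power for these effects runs from above 99% down to 17% at N = 192, so a reader cannot tell from the sentence which benefit the trial can detect.

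Three stronger conclusions are tempting and are not supported:
- That the trial is underpowered. This would be so only if a steady gap of about 1 point were the target and Intervention × Time the deciding test; the documents do not state that target.
- That the power for f = 0.1 is wrong. It reproduces at alpha 0.05.
- That the authors used a between-arm main effect by mistake. A constant 1-point gap does give a main-effect f of (1/2)/5 = 0.1, but the origin of the figure cannot be known from the documents.

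The conclusion rests on the stated SD of 5 and correlation of 0.3, equal arms, T1 as a pre-intervention baseline, and alpha 0.05. That the printed 0.5 is a misprint is an inference; as printed it is not a usable significance threshold.

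**What to change.** 1. Replace the point-per-time-point wording. Either give the pattern that f = 0.1 represents (an arm gap varying over the six times with an SD of 1.0 point, for example widening about 0.59 points per visit, or a steady gap of about 2.7 points from T2), or state the assumed arm difference at each visit and recompute f and power from it.
2. Correct alpha to 0.05. State power for f = 0.1 as about 90% (89.8%) at N = 192 and about 96% at N = 240, before clustering and missing data. The Aim 2 sentence uses the same effect size and should be recalculated at the same alpha; that is a separate point.

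Both items cost wording only, plus a short recalculation if the pattern is changed. The visit labels should follow one schedule: Purpose and Objectives says "The EPDS and GAD-7 will be administered at three time points during pregnancy and at 2, 4, and 6 months postpartum", which has to be reconciled with the T1 to T6 schedule used here.

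Optional, as a design choice and not the repair of an error: if the team expects a steady post-intervention gap, it could name the 1-df, T1-adjusted average difference over T2 to T6 for EPDS as the deciding test, with about 1.2 points detectable at 80% power and 1.4 at 90% (N = 192, correlation 0.3). No new data are needed, but the choice must be fixed before outcome data by arm are seen. The price is lower power for late or brief effects at N = 192. For 2 points at the last two visits only, power is 46% against 85% for Intervention × Time; for 2 points at a single post-intervention visit, 15% against 63%. A team that expects such an effect should keep Intervention × Time and state its pattern.

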## **Statistical Methods, Data Analysis and Interpretation**

---

Enrollment and randomization will continue until the following enrollment goals are met: Urban Latinas = 60 (n = 30 VCI; 30 AC); Rural Latinas = 60 (n = 30 VCI; 30 AC); Urban, North European-descent (NED) = 60 (n = 30 VCI; 30 AC); Rural NED = 60 (n = 30 VCI; 30 AC), for a total of 240 participants.

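### Aim 2 is credited with more than 80% power, but at alpha 0.05 the plan's own inputs give 57% to 69% within a subgroup, and the VCI-by-subgroup interaction has no power statement

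*Combined protocol and SAP*

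**What the plan says.** The power statement is in the Data Analysis section under Study Procedures.

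- **Method.** It names the software ("Sensitivity analysis was conducted with G-Power 3.1") and the approach: "We used RMANOVA with 6 total measures as a conservative power analysis for our mixed-effects model".
- **Target effect.** "The sample is powered for the fixed effect of Intervention X Time".
- **Aim 1.** The inputs are "Using RMANOVA with alpha = 0.5, 6 total measures, 0.3 for correlation between repeated measures, and a sample size of 192 total participants". These are said to give more than 90% power for an effect size of 0.1.
- **Aim 2.** For the samples stratified by location or ethnicity, "we have greater than 80 percent power to detect the same Intervention X Time effect size of 0.1". No N, number of groups or degrees of freedom accompanies this figure.

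The enrolment goals, under Statistical Methods, Data Analysis and Interpretation, set four cells of 60. The first two read "Urban Latinas = 60 (n = 30 VCI; 30 AC); Rural Latinas = 60 (n = 30 VCI; 30 AC"), and the two NED cells are the same size, for 240 in total.

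Purpose and Objectives defines Aim 2 as a difference between subgroups: "Evaluate the interaction of the VCI with specific subgroups: ethnicity (Hispanic, North European descent), geographic location (rural, urban").

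**The concern.** Two things do not fit.

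First, the same effect size and the same test are claimed to have more than 90% power in 192 women and more than 80% in a subset of the trial. A single level of ethnicity or location is half the sample. Halving N halves the non-centrality parameter, and a test sitting near 90% power should then fall well below 80%. The printed alpha of 0.5 hides this, because at that alpha almost any sample looks well powered.

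Second, the quantity powered is not the quantity Aim 2 asks about. Intervention x Time within a stratum shows whether VCI works in that stratum. Aim 2 asks whether it works differently across strata, which is a VCI x subgroup (x time) term.

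Aim 2 is one of two main aims, and the oversampling and four-cell enrolment are built around it. A reader who trusts the 80% could take a null result in Hispanic or rural women as evidence of no benefit, or a null interaction as evidence of equal benefit. The design supports neither reading at the strength claimed.

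**Working it through.** **Inputs.** Effect size f = 0.1, m = 6 measures, correlation ρ = 0.3, N = 192 for Aim 1 (all from the Data Analysis power statement). Cells of 60, so at most 2 × 60 = 120 women in any level of ethnicity or location (enrolment goals). Assumptions: k = 2 arms, sphericity (ε = 1), and, because no Aim 2 sample size is printed, a lower value of 192/2 = 96 per level.

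**Formula** (G\*Power, repeated-measures ANOVA, within-between interaction):

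- λ = f² · N · m / (1 − ρ) = 0.01 × N × 6 / 0.7
- df1 = (k − 1)(m − 1) = 5
- df2 = (N − k)(m − 1) = 5(N − 2)
- Power = P(noncentral F(df1, df2, λ) > critical F at alpha)

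**Step 1: the Aim 1 figure.** At N = 192, λ = 16.46 with df 5 and 950.

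- Alpha 0.05: power 89.8%.
- Alpha 0.5 as printed: power 99.6%.

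The 0.05 reading lands on the stated 90% boundary (N = 194 clears it), so the formula matches the plan's method and 0.05 is the likely intended alpha.

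**Step 2: the Aim 2 figure, same formula.**

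| N in one level | λ | df | Power, alpha 0.05 | Power, alpha 0.10 | Power, alpha 0.5 |
|---|---|---|---|---|---|
| 96 (assumed) | 8.23 | 5, 470 | 57.3% | 69.4% | 94.7% |
| 120 (ceiling) | 10.29 | 5, 590 | 68.7% | 79.0% | 97.2% |

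Of these three alphas, only the printed 0.5 gives more than 80%.

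**Step 3: what 80% would take.** At alpha 0.05, with one input changed at a time:

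- N: 151 is the smallest (80.1%), so 152 with equal arms, against a ceiling of 120.
- Alpha: about 0.184 at N = 96, or 0.107 at N = 120.
- Correlation: about 0.56 at N = 96, or 0.44 at N = 120, in place of 0.3.
- Effect size: f of about 0.126 at N = 96, or 0.113 at N = 120 (rounded up).

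**Step 4: the interaction Aim 2 names.** The documents give no effect size or power for it, so there is no figure to reproduce. As an illustration only, with a scenario of our own: if f = 0.1 in one subgroup and 0 in the other, the three-way term has f = 0.05. With four arm-by-subgroup cells, power on 5 df is 30% at N = 192 and 37% at N = 240. On a 1-df slope it is 53% and 62%.

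**The case against.** The strongest reply is that the Aim 2 sentence leaves its basis open, and some readings do pass 80%.

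- **Four arm-by-stratum groups in the whole trial.** With k = 4 (15 df), power is 83.8% at N = 240. The same run gives 72.1% at the 192 used for Aim 1. A 15-df omnibus test is neither the Intervention x Time effect named in the sentence nor the VCI-by-subgroup interaction. It may explain where the figure came from, but it does not support the claim as written.
- **A 1-df linear slope in the mixed model.** If all of f = 0.1 lies in the slope, power is 81.7% at 96 and 89.3% at 120 (81.0% and 88.9% with N − 2 error df). The plan calls its RMANOVA conservative, which leans this way. But it specifies neither linear time nor a slope test, and does not quantify how conservative the RMANOVA is.
- **The value 96 is not in the documents.** That is correct: it is half of 192. The document-based figure is 69% at 120, and the conclusion does not need the lower one.
- **The Aim 1 shortfall is trivial.** Agreed: 89.8% against 90% is rounding. It matters here only as evidence for the intended alpha.

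What stands is that the origin of the Aim 2 figure cannot be determined from the text. None of these replies supplies power for the interaction as Aim 2 defines it.

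**Conclusion.** The concern holds. Under the stated RMANOVA at alpha 0.05, the stated test would miss f = 0.1 within a subgroup about 31% of the time at full enrolment with no dropout, and about 43% of the time if 96 women are analysed. The plan implies less than 20%. No enrolment within the stated goals reaches 80%.

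This rests on reading alpha as 0.05, a two-arm comparison within one level, the default 5-df test and sphericity. If alpha really is 0.5, the power figures are met, but the test then has a 50% false-positive rate.

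The second part, that Aim 2's own interaction has no power statement, depends on none of these assumptions. Because the figure supports a main aim and is wrong as written, it must be corrected.

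**What to change.** Rewrite the power paragraph in the Data Analysis section under Study Procedures:

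1. Correct alpha to 0.05 and describe Aim 1 power at 192 as about 90 percent.
2. State the N, number of groups, test and degrees of freedom for Aim 2. If the 5-df RMANOVA within a level is meant, replace the claim with wording such as: *about 69 percent power for f = 0.1 with 120 women in a subgroup level (about 57 percent if 96 are analysed); 80 percent power is reached at f of about 0.113 (120) or 0.126 (96).* The sponsor should substitute its own expected analysed N for our assumed 96. If a 1-df slope test or a four-group analysis was intended, say so and give its power on the N that will be analysed.
3. Name the VCI x subgroup (x time) term as the Aim 2 test and say that it is not powered at the level now claimed. Report its estimate with a confidence interval, and state that a null interaction will not be read as equal benefit.

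The cost is one paragraph of wording and a less favourable stated power. It needs no extra participants, visits or data.

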## **Dissemination Plan**

Sharing of data generated by this project is an essential part of our proposed activities and will be carried out in several different ways. We are interested in our results being available to the community of scientists interested in maternal-fetal medicine, health communication, and ethical and social implications of population-level genetic screening. We will register this project with clinicaltrials.gov upon notification of award, in accordance with NIH policy. The Project Administrator will be expected to update the clinicaltrials.gov listing every 6 months, or as needed during recruitment.

We also plan to present our findings at conferences and publish the findings.

### **Procedures performed for research purposes only:**

Group Videoconference Intervention Sessions (UPLIFT Manualized Program): All sessions will be facilitated by a credentialed mental health professional specifically trained in the UPLIFT program. Each 1-hour session will include a check-in, instruction, skill building, discussion. The facilitator will use an UPLIFT manual as the outline for each specific session of the 8-week series. Each participant will also receive the UPLIFT manual (print and/or electronic document), which contains details and resources for each session. Sessions will focus on increasing knowledge about depression and pregnancy, CBT, and MBP. Participants will learn and practice skills related to CBT and mindfulness, and engage in discussions and group exercises for each session's main topic. Topics include thought monitoring, identify distortions in thoughts, self-esteem, identification of problems, goal setting, and achieving support. Exercises include relaxation; body scan; progressive muscle relaxation; attention to breath, sights, and sounds; and meditation. Each week, participants will be provided with

recommendations for between-session practices, which will be discussed at the beginning of the next class.

Attention Control Group (delivered by group videoconference platform): The education program for women  $\geq 32$  weeks gestation is manualized and designed to enhance participant knowledge related to pregnancy, childbirth, newborn care, and feeding. The education program for women  $> 32$  weeks gestation is designed to enhance knowledge related to parenting and young babies. All participants in the AC groups will receive a mailed hard copy and/or emailed electronic packet (participant's choice) that includes topical education, which will also include information about perinatal depression and mood disorders (e.g., anxiety and obsessive-compulsive disorder, postpartum psychosis), interpretation of EPDS scores, common therapies for PD, local resources for obtaining therapies, and encouragement to discuss their EPDS scores with their prenatal care provider.

Participant-Completed Questionnaires. Questionnaires will be completed by participants via a secure, Web-based data management system (REDCap). Women in all study groups will receive an emailed link to the questionnaire. Study questionnaires are to be completed at six time points: T1 = enrollment; T2 = post intervention ; T3 = 2 months post intervention GA; T4 = 4 months post intervention; T5= 6 months post intervention; T6= 8 months post intervention. In addition to participant demographics, questionnaires will include the EPDS as a measure of the primary outcome of interest: depressive symptoms, as well as the GAD-7 as a measure of comorbid anxiety. To document the standard of care that all participants receive during study participation, the questionnaire at all six-time points also asks participants to report whether they (1) received a diagnosis of depression, anxiety, or other mental health condition; (2) were prescribed or initiated any medication for depression or anxiety; (3) were referred to and/or engaged in mental health services; and/or (4) have engaged in any type of nonpharmacological therapies for depression/anxiety during the study. If a participant does not have an email address, study staff will assist her to establish and access a free email address. All participants will receive instruction on how to access and complete the study questionnaires. The entire questionnaire takes approximately 15 minutes to complete. Participants receive \$20 for each questionnaire completed.

